1.0 SUMMARY

Sponsor: Advaxis, Inc.	Name of Finished Product: ADXS11-001 MEDI4736	Type of Treatment: ADXS11-001: Lm-LLO Immunotherapy MEDI4736: MEDI4736 is a human monoclonal antibody (mAb) of the IgG1κ subclass that inhibits binding of programmed cell death-1 ligand (PD-L1) to programmed cell death-1 (PD-1) and CD8
Study Title:	Phase 1-2 Study of ADXS11-001 or MEDI4736 Alone or In Combination In Recurrent/ Metastatic Cervical or HPV+ Head & Neck Cancer	
Trial Phase	Phase I/II	
Clinical Indication	Locally advanced, or metastatic squamous or non-squamous carcinoma of the cervix or HPV+ squamous cell carcinoma of the Head and Neck	
Trial Type	Interventional	
Study Centers	Multicenter, US-only	
Route of Administration	Intravenous (IV)	
Trial Blinding	Open label, unblinded	
Number of Trial Subjects	Approximately 66 
• 6-18 in Phase 1 (Part A) portion of study• 48 in Phase 2 (Part B) portion of study	
Estimated Duration of Trial	Approximately 4 years	
Duration of Participation	Each subject will participate in the trial for up to 4 years from the time the subject signs ICF through the final contact. Treatment will continue for up to 1 year or until the subjects has either documented progression, unacceptable adverse events, withdrawn due to investigator's discretion, subject withdraws consent, pregnancy, or noncompliance with study procedures or treatments. During treatment, subjects who achieve a CR should receive at least 1 additional cycle of treatment. Subjects who stop study treatment after a CR may be eligible for an additional 1 year of study retreatment if they progress within 1 year of stopping study treatment and the study is open. After the end of treatment, each subject will be followed for adverse events for a minimum of 30 days and for serious adverse events for 90 days.	
Randomization Ratio	There is no randomization in the Part A portion of the study. The Part B portion of the study will have a 1:1:2 randomization of ADXS11-001: MEDI4736: ADXS11-001+MEDI4736, respectively	

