5.7.2 Contraception

The study drug(s) may have adverse effects on a fetus in utero. Furthermore, it is not known if the study drug(s) has transient adverse effects on the composition of sperm. Non-pregnant, non-breast-feeding women may be enrolled if they are willing to use 2 methods of birth control or are considered highly unlikely to conceive. Highly unlikely to conceive is defined as 1) surgically sterilized, 2) postmenopausal (has not had menses for greater than 1 year), or 3) not heterosexually active for the duration of the study. The 2 birth control methods can be either 2 barrier methods or a barrier method plus a hormonal method to prevent pregnancy. Males may enroll if they are willing to use 1 method of birth control. Subjects should start using birth control from screening throughout the study period up to 120 days after the last dose of study therapy.

The following are considered adequate barrier methods of contraception: diaphragm, condom (by the partner), copper intrauterine device, sponge, or spermicide. Appropriate hormonal contraceptives will include any registered and marketed contraceptive agent that contains an

estrogen and/or a progestational agent (including oral, subcutaneous, intrauterine, or intramuscular agents).

Subjects should be informed that taking the study medication may involve unknown risks to the fetus (unborn baby) if pregnancy were to occur during the study. In order to participate in the study they must adhere to the contraception requirement (described above) for the duration of the study and during the follow-up period defined in Section [7.2.2](#) - Reporting of Pregnancy and Lactation to the Sponsor. If there is any question that a subject will not reliably comply with the requirements for contraception, that subject should not be entered into the study.

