6.2 Trial Flow Chart for ADXS11-001 Monotherapy (Part B)

Trial Period:	Screening Phase		Treatment Period								Follow up		
Treatment Cycle/Title:	Pre-screening	Screening	Wk 1	Wk 2	Wk 3	Wk 4	Wk 5	Wk 6	Wk 7	Wk 8	Discon	Follow-up Phone Call ²	Follow Up
Scheduling Window (Days):		-28 to -1	$\pm 3^1$				± 3				At time of Discon	30/90 days post discon	Every 8 weeks post discon
Administrative Procedures													
Pre-screening Consent (H&N Subjects only)	X												
HPV+ Test (H&N subjects only)	X												
Informed Consent		X											
Inclusion/Exclusion Criteria		X											
Subject Identification Card		X											
Demographics and Medical History		X											
Prior and Concomitant Medication Review		X	X				X						
ADXS11-001 Administration (Q4wk) ³			X				X						
Clinical Procedures/Assessments													
Review Adverse Events			X				X				X	X	
Physical Examination ⁴		X	X				X				X		
Vital Signs and Weight ⁵		X	X				X				X		
ECOG Performance Status		X	X				X				X		
Tumor Imaging ⁶			X	X							X		X
Laboratory Assessments⁷													
Pregnancy Test – Urine or Serum β -HCG		X	X				X						
PT/INR and aPTT		X	X				X				X		
CBC with Differential		X	X				X				X		
Comprehensive Serum Chemistry Panel		X	X				X				X		
Urinalysis		X	X				X				X		

Trial Period:	Screening Phase		Treatment Period								Follow up		
	Pre-screening	Screening	Wk 1	Wk 2	Wk 3	Wk 4	Wk 5	Wk 6	Wk 7	Wk 8	Discon	Follow-up Phone Call ²	Follow Up
Treatment Cycle/Title:													
Scheduling Window (Days):		-28 to -1	$\pm 3^1$				± 3				At time of Discon	30/90 days post discon	Every 8 weeks post discon

Tissue/Blood Collection

1 - The +/- 3 day window does not apply to Cycle 1, Week 1. This window is only applicable in all subsequent cycles.

2 - Safety Follow up will be conducted via telephone. Safety Follow up at 30 days (± 1 week) for AEs and at 90 days (± 1 week) for SAEs.

3 - Subjects will receive prophylactic NSAIDS and antiemetics [REDACTED] before each ADXS11-001 infusion. Subjects will also receive a course of oral antibiotics to be started 3 days after each ADXS11-001 infusion

4 - ECG and O₂ saturation by pulse oximetry at baseline screening only

5 - Vital signs are to be monitored [REDACTED] following each ADXS11-001 infusion.

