7.1.4.3 Post-Treatment Visits

7.1.4.3.1 Safety Follow-Up Visit

The mandatory Safety Follow-Up Visit should be conducted approximately 30 days (± 5 days) after the last dose of trial treatment or before the initiation of a new anti-cancer treatment, whichever comes first. All AEs that occur prior to the Safety Follow-Up Visit should be recorded. Subjects with an AE of Grade > 1 will be followed until the resolution of the AE to Grade 0-1 or until the beginning of a new anti-neoplastic therapy, whichever occurs first. SAEs that occur within 90 days of the end of treatment or before initiation of a new anti-cancer treatment should also be followed and recorded.

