7.2 Assessing and Recording Adverse Events

An adverse event is defined as any untoward medical occurrence in a patient or clinical investigation subject administered a pharmaceutical product and which does not necessarily have to have a causal relationship with this treatment. An adverse event can therefore be any unfavorable and unintended sign, symptom, or disease temporally associated with the use of a medicinal product or protocol-specified procedure, whether or not considered related to the medicinal product or protocol-specified procedure. Any worsening (i.e., any clinically significant adverse change in frequency and/or intensity) of a preexisting condition that is temporally associated with the use of the Sponsor's product, is also an adverse event.

The Sponsor's product includes any pharmaceutical product, biological product, device, diagnostic agent or protocol-specified procedure, whether investigational (including placebo or active comparator medication) or marketed, manufactured by, licensed by, provided by or distributed by Advaxis for human use.

Adverse events may occur during the course of the use of Advaxis' product in clinical trials or within the follow-up period specified by the protocol, or prescribed in clinical practice, from overdose (whether accidental or intentional), from abuse and from withdrawal.

Adverse events may also occur in screened subjects during any pre-allocation baseline period as a result of a protocol-specified intervention, including washout or discontinuation of usual therapy, diet, placebo treatment or a procedure.

All adverse events will be recorded from the time the consent form is signed through 30 days following cessation of treatment and at each examination on the Adverse Event case report forms/worksheets. The reporting timeframe for adverse events meeting any serious criteria is described in Section [7.2.3.1](#).

Adverse events will not be collected for subjects during the pre-screening period (for determination of archival tissue status) as long as that subject has not undergone any protocol-specified procedure or intervention. If the subject requires a blood draw, fresh tumor biopsy etc., the subject is first required to provide consent to the main study and AEs will be captured according to guidelines for standard AE reporting.

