7.2.2 Reporting of Pregnancy and Lactation to the Sponsor

Although pregnancy and lactation are not considered adverse events, it is the responsibility of investigators or their designees to report any pregnancy or lactation in a subject (spontaneously reported to them), including the pregnancy of a male subject's female partner that occurs during the trial or within 120 days of completing the trial completing the trial, or 30 days following cessation of treatment if the subject initiates new anticancer therapy, whichever is earlier. All subjects and female partners of male subjects who become pregnant must be followed to the completion/termination of the pregnancy. Pregnancy outcomes of spontaneous abortion, missed abortion, benign hydatidiform mole, blighted ovum, fetal death, intrauterine death, miscarriage and stillbirth must be reported as serious events (Important Medical Events). If the pregnancy continues to term, the outcome (health of infant) must also be reported.

Such events must be reported within 24 hours of awareness to inVentiv Health Clinical Pharmacovigilance (Attn: iHC SAE Reporting; [contact] or email: [contact])

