Hepatic function abnormality is defined as any increase in ALT or AST to greater than $3 \times \text{ULN}$ **and concurrent** increase in bilirubin to greater than $2 \times \text{ULN}$ (i.e., Hy's Law cases). Concurrent findings are those that derive from a single blood draw or from separate blood draws taken within 8 days of each other. Follow-up investigations and inquiries will be initiated promptly by the investigational site to determine whether the findings are reproducible and/or whether there is objective evidence that clearly supports causation by a disease (e.g., cholelithiasis and bile duct obstruction with distended gallbladder) or an agent other than the investigational product(s).

If an event of hepatic function abnormality is considered to be related to a pre-existing condition and does not represent a worsening of this condition and/or is considered to be within the range of normal physiological fluctuation for the subject, the event does not meet the definition of an AE and does not need to be recorded as such.

If the underlying diagnosis for the hepatic function abnormality is known (including progression of pre-existing disease such as primary or metastatic malignancy), the diagnosis should be recorded as an AE/SAE.

In the event a subject develops any of the following AEs, a detailed narrative of the event should be reported as an ECI to the Sponsor within 24 hours:

- Grade ≥ 3 diarrhea
- Grade ≥ 3 colitis
- Grade ≥ 2 pneumonitis
- Grade ≥ 3 hypo- or hyperthyroidism

Subjects should be assessed for possible ECIs prior to each dose. Lab results should be evaluated and subjects should be asked for signs and symptoms suggestive of an immune-related event. Subjects who develop an ECI thought to be immune-related should have additional testing to rule out other etiologic causes. If lab results or symptoms indicate a possible immune-related ECI, then additional testing should be performed to rule out other etiologic causes. If no other cause is found, then it is assumed to be immune-related.

ECIs that occur in any subject from the date of first dose through 90 days following cessation of treatment, or the initiation of a new anticancer therapy, whichever is earlier, whether or not related to the Advaxis' product, must be reported within 24 hours to the Sponsor.

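### Non-serious events of clinical interest are due to Day 90, but the general adverse-event rule and two flow charts ask only for serious events after Day 30, so late ascertainment differs by arm

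*Combined protocol and SAP*

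**What the plan says.** **ECIs.** Section 7.2.3.2 defines ECIs as selected serious and non-serious events and has them entered on the adverse-event forms. It covers "ECIs that occur in any subject from the date of first dose through 90 days following cessation of treatment", related or not, with an earlier stop if new anticancer therapy begins. Section 7.2.3.1 has non-serious ECIs handled like serious adverse events (SAEs), and Section 5.5.1 keeps recording concomitant medication for SAEs and ECIs after Day 30.

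**All adverse events.** Section 7.2: "All adverse events will be recorded from the time the consent form is signed through 30 days following cessation of treatment". The only exception it points to is for serious events: "The reporting timeframe for adverse events meeting any serious criteria is described in Section" 7.2.3.1. The Summary (Section 1.0) says "each subject will be followed for adverse events for a minimum of 30 days and for serious adverse events for 90 days". Sections 2.2, 5.8 and 7.1.4.3.1 also mention only serious events beyond Day 30.

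**Day 30 contact.** Section 7.1.4.3.1 makes it a mandatory visit at 30 days ± 5, or before new anticancer treatment if that comes first, and adds: "All AEs that occur prior to the Safety Follow-Up Visit should be recorded". The flow charts show a telephone call. Section 6.2, footnote 2, and Section 6.5, footnote 3, say "Safety Follow up will be conducted via telephone", with a window of ± 1 week.

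**Day 90 contact.** Those same two footnotes restrict the Day 90 call to SAEs. The charts in Sections 6.1, 6.3 and 6.4 mark adverse-event review in the 90-day column with no such restriction, and Section 7.1.4.3.2 describes a 90-day visit with blood collection for the MEDI4736 and combination arms.

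**Pregnancy.** Section 5.7.2: "Subjects should start using birth control from screening throughout the study period up to 120 days after the last dose of study therapy". Section 7.2.2 asks for pregnancies up to 120 days after completing the trial, "or 30 days following cessation of treatment if the subject initiates new anticancer therapy, whichever is earlier".

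**The concern.** A site working from Section 7.2 and the ADXS11-001 monotherapy chart has no prompt to ask about a non-serious ECI after Day 30. Grade 2 pneumonitis on Day 50 is an example: it must be reported under Section 7.2.3.2, but it lies outside the recording period in Section 7.2 and outside the question put at the Day 90 call. Sites treating MEDI4736 or combination subjects do have a prompt.

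This matters because Section 4.2.4.2 makes safety in all three arms, with ECIs named, the primary safety objective, and Section 8.1 summarises adverse events by treatment without stating a common post-treatment cut-off. If one arm is asked about late non-serious events less fully than the others, a difference between arms can come from the asking. Part B is small and Section 8.2 provides no external monitoring committee, so the by-arm tables will be read closely.

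Two smaller inconsistencies belong with this one. The Day 30 contact has two forms and two windows, and some of the permitted days fall before recording is due to end. Pregnancy reporting and contraception count their periods from different dates, and the reporting period shortens when new therapy starts.

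**Working it through.** The plan states no figure to reproduce here. The check sets the sections side by side and does the day arithmetic, treating cessation of treatment and last dose as the same day.

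**1. Non-serious ECI, Days 31-90**

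| Source | Applies to | After Day 30 |
|---|---|---|
| 7.2.3.2 | any subject | ECI due to Day 90 or new therapy |
| 7.2.3.1 | any subject | non-serious ECI handled like an SAE |
| 7.2 | any subject | only serious events excepted from Day 30 |
| 1.0, 2.2, 5.8, 7.1.4.3.1 | any subject | only SAEs named |
| 6.2 footnote 2 | ADXS11-001 monotherapy | Day 90 call: SAEs |
| 6.5 footnote 3 | retreated subjects | Day 90 call: SAEs |
| 6.1, 6.3, 6.4 | Part A combination; MEDI4736; Part B combination | Day 90: adverse-event review, unrestricted |

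The duty to report to Day 90 is explicit. The general rule and two of the five charts do not carry it through.

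**2. Subjects on each side.** Part B has 48 subjects at 1:1:2 (Section 1.0).
- One share: 48 / 4 = 12.
- ADXS11-001 monotherapy, SAE-only call: 12, or 12/48 = 25%.
- MEDI4736-containing arms, unrestricted review: 12 + 24 = 36, or 36/48 = 75%.
- Retreated subjects add to the SAE-only group whatever their arm. Their number is not given.

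**3. Day 30 contact**
- Section 7.1.4.3.1: 30 ± 5 gives Day 25 to 35.
- Sections 6.2 and 6.5: 30 ± 7 gives Day 23 to 37.
- Sections 6.1, 6.3 and 6.4: telephone call, no window stated.
- Earliest scheduled contact: 30 − 25 = 5 days short of Day 30 under the text, and 30 − 23 = 7 days short under the two charts. A visit brought forward by new therapy can fall earlier still.

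**4. Pregnancy.** Contraception runs to 120 days after the last dose. For a subject who starts new anticancer therapy, reporting stops 30 days after cessation, leaving 120 − 30 = 90 days of the contraception period outside it. For everyone else, reporting runs to 120 days after completing the trial. That is no earlier than 120 days after the last dose, and it may be much later because follow-up lasts up to 3 years (Section 2.2).

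**The case against.** The best defence is that the plan sets tiers deliberately: all events to Day 30, and SAEs and ECIs to Day 90. Sections 7.2.3.1 and 5.5.1 support this, and the 30 days in Sections 1.0 and 2.2 is a minimum, which a longer ECI rule does not breach. The named ECIs are tied to anti-PD-L1/PD-1 agents, and the arms receiving MEDI4736 are asked at Day 90. Section 4.2.3.1 reports no delayed-onset symptoms with the ADXS11-001 class, and no between-arm safety test is planned. Most of this stands: an ECI tier was intended, and the gap is narrow. It does not dispose of the point, because Section 7.2.3.2 applies to any subject regardless of relatedness, and a descriptive comparison of arms still needs the same question asked in each.

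Stronger readings are tempting but unsupported:
- A reader might infer that late immune events are lost. SAEs and the listed ECIs remain reportable to Day 90 or new therapy, and related SAEs at any time. The risk is of not asking.
- A reader might infer that recording ends on Day 23-25. Section 7.2 still requires recording through Day 30, and Section 7.1.4.3.1 does not exclude events after an early visit.
- A reader might divide 60 days by 90 and say two thirds of the ECI window is unrecorded. That window opens at first dose, so 90 days is the wrong denominator.
- A reader might infer that pregnancy reporting generally stops at Day 30. It does so only if new anticancer therapy starts.
- A reader might conclude that Day 90 chemistry and thyroid tests are missing. Section 7.2.3.2 ties routine ECI laboratory review to dosing, with further testing when findings suggest an event. The 90-day blood list is also partly redacted. New tests would be an added procedure, not a correction.

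**Conclusion.** The point holds as an inconsistency in safety ascertainment. The Day 90 duty for non-serious ECIs is clear in Section 7.2.3.2, but it is missing from the general recording rule, from four other sections and from two flow-chart footnotes. Followed as written, about 12 of 48 Part B subjects are asked only about SAEs at Day 90, while about 36 have an unrestricted review. Late non-serious ECIs are then more likely to be missed on ADXS11-001 monotherapy, which would bias a descriptive comparison in that arm's favour.

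The number of events affected cannot be stated, because the documents give no late-event rate. The arm counts assume exact 1:1:2 allocation and that the extracted charts show the 90-day column correctly.

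The Day 30 contact can precede the end of recording by 5 to 7 days, or by more if new therapy starts. This is a weakness in prompting only. The pregnancy mismatch is real but conditional on new anticancer therapy, together with a difference in the date from which the 120 days are counted.

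**What to change.** - Name ECIs, serious or not, beside SAEs in Sections 1.0, 2.2, 5.8, 7.1.4.3.1 and 7.2, and in footnote 2 of Section 6.2 and footnote 3 of Section 6.5.
- Ask about both SAEs and ECIs at the Day 90 contact in every arm and after retreatment. Keep the existing cut-off at new anticancer therapy.
- Set one form and one window for the Day 30 contact across Section 7.1.4.3.1 and all charts, so that it covers events through Day 30.
- Reconcile Section 7.2.2 with Section 5.7.2 on the starting date of the 120 days and on the shortening after new therapy. Do not shorten the default reporting window: a flat 120 days from the last dose could do so, because the present default runs from trial completion.

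The cost is protocol wording, changed case-report-form prompts and a few more late events to process. No new visit, sample or laboratory test is needed.

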7.2.4 Evaluating Adverse Events

An investigator who is a qualified physician will evaluate all adverse events according to the NCI Common Terminology for Adverse Events (CTCAE), version 4.0. Any adverse event which changes CTCAE grade over the course of a given episode will have each change of grade recorded on the adverse event case report forms/worksheets.

All adverse events regardless of CTCAE grade must also be evaluated for seriousness.

The following attribution categories will be used in assessing the relationship between the AE and the study drug:

Table 10 Evaluating Adverse Events

RELATIONSHIP	ATTRIBUTION	DESCRIPTION
Unrelated to investigational agent/intervention	Unrelated	The AE is clearly NOT related to the intervention
	Unlikely	The AE is doubtfully related to the intervention
Related to investigational agent/intervention	Possible	The AE may be related to the intervention
	Probable	The AE is likely related to the intervention
	Definite	The AE is clearly related to the intervention

7.2.5 Sponsor Responsibility for Reporting Adverse Events

All Adverse Events will be reported to regulatory authorities, IRB/IECs and investigators in accordance with all applicable global laws and regulations.

8.0 STATISTICAL ANALYSIS PLAN

8.1 Statistical Analysis Plan Summary

This is a Phase 1-2 study of ADXS11-001 or MEDI4736 alone or combination in locally advanced, or metastatic, squamous or non-squamous carcinoma of the cervix or HPV+ squamous cell carcinoma of the head and neck.

There are 2 phases in this study with different objectives. For safety, the analysis will be performed for Part A and Part B separately and combined. The efficacy analysis will be performed for Part A and Part B separately. SAS 9.2 or higher will be used for data analysis.

Subject disposition, demographic and baseline subject characteristics will be summarized separately for Part A and Part B. Adverse events will be classified and summarized by type, incidence, severity, and causality. All adverse events will be summarized by subject, treatment, and disease. All subjects who receive at least 1 dose of study treatment will be included in the safety analyses.

Statistical analysis for efficacy will be summarized by treatment arm and disease type. Although it may lack statistical power, statistical testing for treatment comparisons will be performed as a reference. Tumor response will be evaluated by RECIST criteria and secondarily by irRECIST criteria. The overall response rate will be summarized; frequency counts and percentage and will be tested by the Fisher's Exact test. PFS is defined as the time from randomization until objective tumor progression or death. Subjects who have not progressed or who are still alive at the time of evaluation will be censored for the analysis. Kaplan-Meier (KM) curves and descriptive statistics will be used to summarize PFS. The percentage of subjects with PFS and the 95% confidence intervals will be provided. PFS and duration of response will be summarized using KM method and tested by the Log-Rank test controlled by disease type.

Furthermore, the disease response will be tabulated for all subjects who receive ADXS11-001 monotherapy, MEDI4736 monotherapy or ADXS11-001 + MEDI4736 combination therapy.

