Methodology	This is a 2 part study in subjects with either metastatic squamous or non-squamous carcinoma of the cervix or metastatic HPV+ squamous cell cancer of the head and neck (SCCHN). Part A of the study is a Phase 1 dose escalation evaluation of the combination of ADXS11-001 and MEDI4736. The Phase 1 portion of the study will utilize a “3+3” design which will dictate dose escalation and de-escalations. Once a maximum tolerated dose is identified and subjects from Part A have been followed for the 28-day DLT period, Part B of the study will commence. Part B of the	

Sponsor: Advaxis, Inc.	Name of Finished Product: ADXS11-001 MEDI4736	Type of Treatment: ADXS11-001: Lm -LLO Immunotherapy MEDI4736: MEDI4736 is a human monoclonal antibody (mAb) of the IgG1κ subclass that inhibits binding of programmed cell death-1 ligand (PD-L1) to programmed cell death-1 (PD-1) and CD8
		study will be a Phase 2 randomized design where subjects will be randomized 1:1:2 to ADXS11-001: MEDI4736: ADXS11-001+MEDI4736. Stratification will be based upon disease type. Safety will be assessed at every visit by comparing treatment-related adverse events (AEs), changes in physical examinations, vital signs measurements, and laboratory abnormalities.
Criteria for Evaluation		Safety: recorded AEs, changes in physical examinations, vital signs measurements and clinical laboratory evaluations Efficacy: Response rates as measured by RECIST 1.1 and irRECIST, duration of response, PFS

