4.2.4.2 Safety Endpoints

The primary safety objective of this trial is to characterize the safety and tolerability of ADXS11-001 alone, MEDI4736 alone, and ADXS11-001 in combination with MEDI4736 in subjects with previously treated locally advanced or metastatic SSCHN or cervical cancer. The primary safety analysis will be based on subjects who experience toxicities as defined by NCI CTCAE v 4.03. Safety will be assessed by quantifying the toxicities and grades, including SAEs and events of clinical interest (ECI) experienced by subjects who have

received ADXS11-001, MEDI4736, or ADXS11-001 + MEDI4736 combination therapy. The attribution to drug, time-of-onset, duration of the event, its resolution, and any concomitant medications administered will be recorded. AEs will be analyzed including but not limited to all AEs, SAEs, fatal AEs, and laboratory changes.

4.2.4.3 [REDACTED]

[REDACTED]

[REDACTED]

[REDACTED]

[REDACTED]

[REDACTED]

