7.1.4.1 Screening

Screening period – will start when the first screening evaluation is performed. This does not include signing of Informed Consent or wash out periods. Screening evaluations will be performed within 28 days prior to the first treatment administration, unless otherwise specified.

Informed Consent - each subject must sign a copy of the most current IRB/IEC approved informed consent document. A copy of the signed document will be maintained with the subject's records.

Inclusion/Exclusion Criteria - all inclusion and exclusion criteria will be reviewed by the Investigator or qualified designee to ensure that the subject qualifies for the trial

Medical History/Prior and Concomitant Medications - past or current medical conditions, current medications, medications taken within 28 days of study entry, histological confirmation of cancer, tumor staging (refer to the most current American Joint Committee on Cancer Staging Manual, the fifth edition or higher), and prior cancer therapies and best response(s), if applicable.

Complete physical exam - including baseline ECG and O₂ saturation by pulse oximetry

Pregnancy test - A rapid pregnancy test will be performed for all women of child bearing potential. A positive rapid pregnancy test must be confirmed by serum.

HPV genotyping – specimen collection for confirming HPV+ will be collected for SCCHN subjects, if necessary. Details regarding collection, preparation and shipping specimen can be found in the laboratory manual.

Laboratory Procedures (hematology, chemistry, urinalysis, other) – must be performed within 28 days prior to first dose of study treatment. Screening lab that are done within 5 days of initiating treatment can be used for C1D1 laboratory tests.

Tumor Imaging/Disease Assessment - CT scan or MRI for determination of unidimensional measurements and disease response. Baseline tumor imaging/disease assessment must be performed within 28 days prior to the first dose of study treatment.

Analysis of [REDACTED] – [REDACTED]

[REDACTED]
[REDACTED]
[REDACTED]
[REDACTED]
[REDACTED]

[REDACTED]

Correlative studies: Blood will be collected as indicated in Section [7.1.2.13.2](#).

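### Section 8.1 summarises all adverse events as crude incidence by arm, so descriptive differences between arms partly reflect time at risk, and pre-dose and retreatment events are not separated

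*Combined protocol and SAP*

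**What the plan says.** **Measure.** Section 8.1: "Adverse events will be classified and summarized by type, incidence, severity, and causality. All adverse events will be summarized by subject, treatment, and disease". The denominator is everyone treated: "All subjects who receive at least 1 dose of study treatment will be included in the safety analyses". Section 4.2.4.2 adds: "The primary safety analysis will be based on subjects who experience toxicities as defined by NCI CTCAE v 4.03". Together these describe a crude proportion of subjects.

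**Collection window.** Section 7.2: "All adverse events will be recorded from the time the consent form is signed through 30 days following cessation of treatment". SAEs run from consent (7.2.3.1) and events of clinical interest from first dose (7.2.3.2). Both continue to 90 days after treatment, or to new anti-cancer therapy if that comes sooner.

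**Time before first dose.** Screening evaluations fall within 28 days before treatment, but Section 7.1.4.1 says of the screening period: "This does not include signing of Informed Consent or wash out periods". Consent can therefore precede first dose by more than 28 days.

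**Time on treatment.** Section 2.2 ends treatment at progression, unacceptable toxicity, other listed reasons, or 1 year. Section 7.1.4.2.1 allows up to one further year of retreatment under conditions.

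**Not found.** There is no treatment-emergent definition, common between-arm window, person-time rate, cumulative incidence or rule for retreatment AEs. Section 4.2.4.2 does require time of onset to be recorded.

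**The concern.** Safety of the combination is a Part B primary objective (Section 3.4), and so is PFS. The trial therefore looks for differences in the quantity that largely sets how long each subject is observed for AEs. If one arm delays progression, its subjects are watched longer and more of them will have at least one event, even at the same event rate. If an arm fails early, real toxicity can be under-represented. No AE test is named, but the arm tables are what readers and the internal safety review team (Section 8.2) will look at side by side.

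Separately, a table of all AEs by treatment places events under an arm before any drug of that arm was given. It also mixes retreatment events with those of the initial course.

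**Working it through.** The plan states no AE rate, treatment duration or AE power figure, so there is nothing of its own to reproduce. Part B has 48 subjects at 1:1:2, which gives 12/12/24.

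**Model (assumptions).** The AE hazard h per month is constant and the same in every arm. Time to stopping is exponential with μ = ln 2 / median, capped at 12 months. Collection continues for 1 further month (about 30 days). The clock starts at first dose.

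Crude incidence = 1 − e^(−h) × [ μ/(μ+h) + h/(μ+h) × e^(−12(μ+h)) ]

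**Worked case, h = 0.10.**
- Median 3: μ = 0.2310. The bracket is 0.6979 + 0.3021 × 0.0188 = 0.7036. Incidence = 1 − 0.9048 × 0.7036 = 36.3%.
- Median 6: μ = 0.1155. The bracket is 0.5360 + 0.4640 × 0.0753 = 0.5710. Incidence = 1 − 0.9048 × 0.5710 = 48.3%.

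Mean time at risk = (1 − e^(−12μ))/μ + 1. This is 0.9375/0.2310 + 1 = 5.06 months and 0.75/0.1155 + 1 = 7.49 months.

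The standard error is √[p₁(1−p₁)/12 + p₂(1−p₂)/24]. At h = 0.10 it is √(0.0193 + 0.0104) = 0.17.

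| h per month | Median 3 | Median 6 | False gap (points) | SE of difference, 12 vs 24 (points) |
|---|---|---|---|---|
| 0.05 | 21.2% | 29.7% | 8.5 | 15 |
| 0.10 | 36.3% | 48.3% | 12.0 | 17 |
| 0.20 | 55.9% | 68.8% | 12.9 | 17 |

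**Longer tail.** With a full 90-day (3-month) tail and h = 0.10, the gap is e^(−0.3) × (0.7036 − 0.5710) = 0.741 × 0.1326 = 9.8 points. The longer SAE and ECI window shrinks the effect but does not remove it.

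**Ranking of arms.** These are simulated trials with arms of 12/12/24, equal hazards of 0.05 to 0.20 and 40,000 replicates.

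| Assumed medians (months) | Combination strictly highest |
|---|---|
| 2/2/2 | 26-27% |
| 3/3/4 | 36-39% |
| 2/3/6 | 57-66% |

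**Early events only.** If the same risk (0.2 per month) acts only in the first 28 days, with medians 2/3/6, crude incidence is already equal at 16.8/16.9/16.8%. First events per subject-month are then 0.052/0.040/0.027, which flatters the longest-treated arm. Under a constant hazard of 0.10 the same rate measure gives 0.100/0.100/0.100. Person-time is therefore right for accruing events and misleading for early ones.

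**Pre-dose events.** The documents give no basis for a number, so this part is not quantified.

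**The case against.** The AE analysis is descriptive. The testing sentences in Section 8.1 concern efficacy, the Part B safety objective states no contrast between arms, and Section 4.2.4.2 speaks of characterising safety. The share of treated subjects who ever have an event is a legitimate description. The Summary does say "Safety will be assessed at every visit by comparing treatment-related adverse events (AEs", but alongside examinations, vital signs and laboratory results this reads most naturally as visit-by-visit monitoring. This stands: the plan misstates nothing and no AE test is affected.

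A constant hazard is also doubtful for ADXS11-001. Section 5.2.1.3 places most of its infusion symptoms within 6 hours and reports no cumulative toxicity. This stands in part, because such symptoms can recur at each infusion and the chance of at least one can still grow with the number of infusions.

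The pre-dose problem is partly contained. Exclusion 1 requires recovery from earlier toxicity to Grade 1 or baseline, AEs are also summarised by causality, and the flow charts begin AE review at Week 1. Section 7.2 nevertheless records from consent, and Section 8.1 takes all AEs.

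A reader might infer three stronger things that the documents do not support:
- **That the longest-treated arm will look most toxic.** The effect holds in expectation only, and the documents do not say which arm stays on treatment longest.
- **That pre-dose events bias the arm comparison.** In randomised Part B they should be balanced in expectation.
- **That dose selection is affected.** Part A DLTs use a fixed 28-day period from first dose (Section 5.2.1.2).

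**Conclusion.** The point holds as a reporting weakness. Crude incidence by arm, collected over a window that lengthens with treatment, mixes event rate with time at risk. The expected false gap is about 9 to 13 points if hazards are equal and constant at 0.05 to 0.20 per month and median treatment is 3 versus 6 months. All of these are assumptions. The gap is zero if durations are equal or events are confined to the first weeks. At 12 versus 24 subjects it is below one standard error of the difference, so it would not by itself settle how the arms look. The effect of retreatment was not computed and applies only to subjects who meet the conditions in Section 7.1.4.2.1. Pre-dose events add noise in Part B rather than bias between arms. The change is worth making because it is cheap, not because a stated figure is wrong.

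**What to change.** In Section 8.1:

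1. Limit AE tables by arm to events that start or worsen after the first dose of the initial course. List pre-dose events and retreatment events separately.
2. Keep crude percentages as description.
3. Add incidence in the first 8-week cycle (Day 1-56) together with cumulative incidence over time. Day 1-56 is nearly a common window: the first on-treatment imaging is at Cycle 2 Week 1 (± 1 week), and AE collection ends before Day 56 only for subjects who stop before about Day 26 (56 − 30) or whose collection is cut short.
4. If events per subject-month are shown, present them only beside the Day 1-56 table, because alone they understate early toxicity in the longest-treated arm.
5. State the 30-day AE window and the 90-day SAE and ECI windows with the tables they govern.

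The cost is SAP wording and a few extra tables from data already collected, since onset time is recorded. No dose, schedule or visit changes.
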